9.5.1.5.3 LABORATORY MEASUREMENTS

Clinical laboratory tests to be performed, including hematology, chemistry, and urinalysis, are summarized in [Table 1](#). Subjects should be in a seated or supine position during blood collection. The Schedule of Procedures/Assessments ([Table 2](#)) shows the visits and time points at which blood for clinical laboratory tests and urine for urinalysis will be collected in the study.

Table 1 Clinical Laboratory Tests (revised per Amendment 01)

Category	Parameters
Hematology	Hematocrit, hemoglobin, platelets, RBC count, and WBC count with differential (bands, basophils, eosinophils, lymphocytes, monocytes, neutrophils)
Chemistry	
Electrolytes	Chloride, potassium, sodium
Liver function tests	Alanine aminotransferase, alkaline phosphatase, aspartate aminotransferase, gamma glutamyl transpeptidase, direct bilirubin, total bilirubin
Renal function tests	Blood urea/blood urea nitrogen, creatinine
Thyroid function	T4, TSH
Adrenal function	AM serum Cortisol
Sex hormones	Testosterone (male subjects), estradiol (female subjects)
Bone health assessments	Serum OC and PICP, Hydroxy-proline; Urine NTX
Prolactin	Fasting prolactin levels
Other (revised per Amendment 01)	Albumin, calcium, globulin, fasting glucose, HbA _{1c} , HDL cholesterol, fasting insulin, lactate dehydrogenase, LDL cholesterol, fasting lipid panel, phosphorus, total protein, total cholesterol, triglycerides, uric acid, urine β -hCG
Urinalysis	Bacteria, casts, crystals, epithelial cells, glucose, ketones, occult blood, pH, protein, RBCs, specific gravity, WBCs

β -hCG = beta-human chorionic gonadotropin, HbA_{1c} = hemoglobin A_{1c}, HDL = high density lipoprotein, LDL = low density lipoprotein, OC = osteocalcin; NTX = N-telopeptide, PICP = carboxyterminal propeptide of type I procollagen; RBC = red blood cell, T4 = thyroxine, TSH = thyroid stimulating hormone, WBC = white blood cell.

Clinical laboratory tests during the study will be performed by a central laboratory. All blood and urine samples will be collected and sent to the central laboratory on the day of collection unless otherwise instructed. In cases of a safety concern, blood samples will be split (or 2 samples drawn) to allow a local laboratory analysis in addition to the central laboratory.

A laboratory abnormality may meet the criteria to qualify as an AE as described in this protocol (see [Section 9.5.1.5.1](#)) and the CRF Completion Guidelines. In these instances, the AE corresponding to the laboratory abnormality will be recorded on the Adverse Event CRF.

9.5.1.5.4 VITAL SIGNS AND WEIGHT MEASUREMENTS

Vital sign measurements (ie, systolic and diastolic BP [mmHg], pulse [beats per minute], respiratory rate [per minute], body temperature [in centigrade]), and weight (kg) will be obtained as designated in the Schedule of Procedures/Assessments ([Table 2](#)) by a validated

method. BP and pulse will be measured after the subject has been sitting for 5 minutes. All BP measurements should be performed on the same arm, preferably by the same person.

When vital signs are to be obtained concurrently with PK or other blood samples, the vital sign measurements will be performed before drawing blood samples in order to maximize the accuracy of blood sampling times while minimizing the potential effects of blood drawing on recordings obtained during safety assessments.

9.5.1.5.5 HEIGHT MEASUREMENTS

Height (cm) measurements will be obtained as designated in the Schedule of Procedures/Assessments ([Table 2](#)).

9.5.1.5.6 CDC GROWTH MEASUREMENTS

Investigators will calculate the height for age percentile and weight for age percentile utilizing the most recent CDC 95th Percentile Growth Chart and the height and weight measurements obtained, as designated in the Schedule of Procedures/Assessments ([Table 2](#)). (revised per Amendment 01)

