- Proportion (%) of subjects achieving at least a 5% and at least a 10% reduction in BMI

Other PD endpoints will be considered based on the data at the end of the study to explore their relationships with lorcaserin plasma exposure.

Pharmacogenomic/Pharmacogenetic Assessments

Not applicable

Safety Assessments

Safety assessments will consist of monitoring and recording all adverse events (AEs) and serious adverse events (SAEs); electrocardiograms (ECGs); laboratory evaluation for hematology, metabolic function (fasting glucose, fasting lipids, and thyroid), adrenal function and biochemical blood and urine bone health assessments; blood chemistry and urine values; neuropsychiatric events; periodic measurement of vital signs, neuromuscular signs for screening potential serotonin syndrome, and signs or symptoms of priapism and hyperprolactinemia; and performance of physical examinations. In patients with potential prolactin-related AEs, such as galactorrhea, changes in libido, or changes to menstrual cycle, prolactin level will be measured and assessed.

Other Safety Assessments

Effect on growth will be evaluated using the CDC growth chart and bone age determination by x-ray of the hand. Sexual maturation will be evaluated by assessing sex hormones and Tanner Staging.

The C-SSRS will be used to assess all subjects in the study for any signal of depression or suicidal ideation or behavior at every visit. Additionally, screening, diagnosing, monitoring, and measuring the severity of depression will be assessed using the PHQ-9 and effects on cognition will be assessed using the Leiter-3. (revised per Amendment 01)

Echocardiographic assessments will be used to exclude subjects with FDA-defined valvulopathy, pulmonary hypertension, and other major cardiovascular disease (as outlined in Exclusion Criterion No. 3) during the Screening Period. Additionally, cardiac valvular function and pulmonary systolic pressure changes at Weeks 28 and 52 will be assessed. Valvular regurgitation as assessed in the echocardiogram will be rated absent, trace, mild, moderate, or severe for the aortic, mitral, and tricuspid valves; the rating will be absent or present for the pulmonic valve. The evaluations will be based on guidelines from the American Society of Echocardiography. Pulmonary artery pressure will be estimated from the TR jet velocity.

Bioanalytical Methods

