9.3.1 Inclusion Criteria

Subjects must meet all of the following criteria to be included in this study:

1. Healthy male or female adolescents, ages 12 to 17 years old at Screening, with a BMI that is greater than or equal to the United States (US)-weighted mean of the 95th percentile based on age and sex with a body weight greater than 60 kg
2. Subjects and their families are not planning to move away from the area for the duration of the study
3. Subjects able and willing to comply with all aspects of the study, including a standardized, reduced-calorie diet and an age-appropriate, increased physical activity program
4. Subjects considered in stable health in the opinion of the investigator
5. Caregivers or guardians meet the following requirements:
 - a. Able and willing to support and supervise study participation in the opinion of the investigator, including consideration of any existing physical, medical, or mental condition that prevents compliance with the protocol
 - b. Able and willing to personally comply with and execute all aspects of the study requirements for the caregivers or guardians

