9.7.1.8.4 VITAL SIGNS

Descriptive statistics for vital signs parameters (eg, systolic and diastolic BP, pulse, respiratory rate, temperature, weight) and changes from baseline will be presented by visit and treatment group.

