9.7.1.8.6 OTHER SAFETY ANALYSES

Other safety assessments including adolescent growth evaluations using 95th percentile CDC growth charts and bone age using x-ray of the hand, sexual maturation as measured in Tanner Staging, study drug effect on cognition assessed by Leiter-3, assessment of suicidality using C-SSRS, and depression assessment using PHQ-9 will be summarized by treatment group at each scheduled visit. For echocardiographic assessments, the proportion of subjects who develop FDA-defined valvulopathy, the proportion of subjects who develop pulmonary hypertension (defined as when a subject's SPAP is ≥ 40 mmHg evaluated by echocardiograph], and change from baseline in SPAP will also be summarized by treatment group at Week 28 and Week 52. (revised per Amendment 01)

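### Growth safety is reported as site-calculated percentiles from a chart named for a single percentile; centrally derived Z-scores, with corrected chart wording, would serve better at little cost

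*Protocol*

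**What the plan says.** Growth measured by CDC growth chart is part of the safety objective in Protocol Section 8.2. Section 9.5.1.5.6 assigns the derivation to the sites: "Investigators will calculate the height for age percentile and weight for age percentile", "utilizing the most recent CDC 95th Percentile Growth Chart". Section 6 puts the number of sites at about 30. Section 9.7.1.8.6 then lists "adolescent growth evaluations using 95th percentile CDC growth charts and bone age using x-ray of the hand" among the assessments to be summarised by treatment group at each scheduled visit. The synopsis is looser and names no percentile: "Effect on growth will be evaluated using the CDC growth chart and bone age determination by x-ray of the hand".

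Other provisions bear on the point:

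- Section 9.5.1.5.5 collects height in centimetres, and Table 2 marks height at every visit.
- Table 2 schedules hand x-rays for bone age at Baseline and Weeks 12, 28 and 52.
- Section 9.7.1.8.4 gives weight as an example of the vital signs to be summarised, but does not mention height.
- Section 9.7.1.6 plans a BMI Z-score analysis as an efficacy sensitivity analysis. No section names a Z-score for growth.
- Section 9.5.1.1 lets age be recorded in place of date of birth.
- Section 9.7.1.8 rules out hypothesis testing on safety data.

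**The concern.** There are three separate weaknesses.

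**Chart wording.** A single 95th percentile curve shows only whether a subject is above or below it. It does not return a percentile such as the 60th or the 98th. Read literally, the instruction cannot be carried out, and sites may resolve it differently.

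**Scale.** A percentile is a bounded, non-linear transform of the standardised score. The same slowing of growth produces a smaller change in percentile the further the subject starts from the middle. Any summary of percentile changes by arm therefore weights equal losses unequally.

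**Place of derivation.** The calculation is left to about 30 sites, although it is a deterministic function of data already in the database.

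What is at stake is how readable a descriptive safety result will be. Of the two measures in Section 9.5.1.5.6, weight-for-age is likely to be the more compressed, and it is also moved by the intended effect of the drug. The growth question therefore rests mainly on height, and no standardised height change is named.

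**Working it through.** The protocol gives no effect size, SD, margin or power for growth, so there is no figure of its own to reproduce. The check is of the scale.

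**Inputs**

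- Measures: height-for-age and weight-for-age percentiles (Section 9.5.1.5.6).
- Entry: age 12 to 17 years, "with a BMI that is greater than or equal to the United States (US)-weighted mean of the 95th percentile based on age and sex", and body weight above 60 kg (Section 9.3.1). There is no criterion on height.
- Assumption: percentile = 100·Φ(z), where z is the age- and sex-standardised score.
- Assumption: a growth loss of d = 0.25 SD. The protocol gives no value, so 0.1 and 0.5 are shown as a range.
- Assumption: a typical height z of 0 to 1. The protocol gives no height distribution.

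**Formula.** Percentile points lost from starting score z₀ = 100·[Φ(z₀) − Φ(z₀ − d)].

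For d = 0.25:

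- z₀ = 0: 50.00 − 40.13 = 9.87
- z₀ = 1: 84.13 − 77.34 = 6.8
- z₀ = 1.645: 95.00 − 91.85 = 3.15
- z₀ = 2.33: 99.01 − 98.12 = 0.89

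| Starting percentile (z₀) | d = 0.1 | d = 0.25 | d = 0.5 |
|---|---|---|---|
| 50th (0) | 3.98 | 9.87 | 19.15 |
| 84th (1) | 2.54 | 6.80 | 14.99 |
| 95th (1.645) | 1.12 | 3.15 | 7.61 |
| 99th (2.33) | 0.30 | 0.89 | 2.37 |

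For very small losses, sensitivity relative to mid-scale is the normal density ratio φ(z₀)/φ(0). It is 0.61 at z₀ = 1, 0.26 at 1.645, 0.135 at 2 and 0.044 at 2.5.

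**Applied to the two measures**

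- *Weight-for-age.* Subjects are selected for high BMI and for weight above 60 kg, so most are expected in the upper part of the scale. At d = 0.25, a subject at the 95th percentile shows 3.15/9.87 = 32% of the change shown by one at the median, and a subject at the 99th shows 0.89/9.87 = 9%.
- *Height-for-age.* Entry does not select on height. For z of 0 to 1, the same loss shows as 9.9 to 6.8 points. The weighting differs by a factor of 9.87/6.80 = 1.45. That is uneven, but the loss remains visible. Strong compression needs a height z near 1.645 or above.

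On a Z-score scale the loss is 0.25 from every starting point.

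**The case against.** The best case against the point has four parts.

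First, slowed growth is read from height, and nothing in Section 9.3.1 places subjects high on the height scale. This stands. A reader might infer that obese adolescents sit at the top of the growth chart and that the trial would therefore struggle to see slowed growth. The entry criteria support that position for weight only, so a 3- to 11-fold loss of sensitivity should not be read across to height.

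Second, growth safety does not rest on percentiles alone. Height in centimetres is taken at every visit, bone age appears in the same sentence of Section 9.7.1.8.6, and Tanner staging, sex hormones and bone markers are collected. This also stands: no information is lost.

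Third, the protocol does not specify a mean change in percentile. It says only that growth will be summarised by arm and visit, with no testing, and the details of a descriptive table normally belong in the SAP, which is not shown and may add a Z-score. This stands in part. An SAP could add the summary, but the site task and the chart wording are affirmative protocol text that an SAP would leave in place.

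Fourth, a reader might suppose that sites will read values by hand off a plotted curve and add reading error. The text says only that investigators will calculate the percentiles and does not say how, so no such error is claimed here.

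**Conclusion.** The point holds as a minor improvement. The chart named in Sections 9.5.1.5.6 and 9.7.1.8.6 cannot by its name yield the percentiles asked for. The percentile scale distorts equal losses: at an assumed 0.25 SD the change runs from 9.9 points at the median to 3.15 at the 95th percentile and 0.9 at the 99th. Strong compression is an expectation for weight-for-age, resting on the entry criteria rather than on a stated weight distribution. For height-for-age it is moderate, 9.9 to 6.8 points, if height z lies between 0 and 1, and severe only for very tall subjects.

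The documents do not support the stronger conclusion that an effect on growth would be missed. The raw measurements and bone age remain available, and no confirmatory test depends on the scale. The sizes rest on the normal link, the assumed loss and the assumed height range. The pattern across starting points does not depend on the size of loss chosen: all three values in the table show it.

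**What to change.** In Sections 9.5.1.5.6 and 9.7.1.8.6:

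1. Replace the reference to a 95th percentile chart with the CDC growth reference.
2. Replace the site calculation with height-for-age and weight-for-age Z-scores derived centrally from recorded height, weight, sex and age at visit.
3. Summarise change from baseline in height Z-score by arm and visit, beside bone age. Keep percentiles as a listing.

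In Section 9.5.1.1, record date of birth rather than allowing age instead, so that age at each visit is exact. The BMI Z-score planned in Section 9.7.1.6 needs the same.

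The cost is a small programming step and the text edits. No visit or measurement is added, and a task is taken away from the sites.

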9.5.1.5.7 WAIST CIRCUMFERENCE

Waist circumference (cm) measurements will be taken 3 times at each visit as designated in the Schedule of Procedures/Assessments ([Table 2](#)). (revised per Amendment 01)

9.5.1.5.8 PHYSICAL EXAMINATIONS

Physical examinations will be performed as designated in the Schedule of Procedures/Assessments ([Table 2](#)). Documentation of the physical examination will be included in the source documentation at the site. Significant findings at the Screening Visit will be recorded on the Medical History and Current Medical Conditions CRF. Changes from screening physical examination findings that meet the definition of an AE will be recorded on the Adverse Events eCRF.

As part of the physical examination, a neuromuscular sign assessment for serotonin syndrome will be performed for potential serotonergic syndrome components. Serotonergic syndromes that meet the diagnostic criteria will be captured by AE eCRF. (revised per Amendment 01)

Signs and symptoms of priapism (painful erection) and hyperprolactinemia (menstrual cycle abnormalities or galactorrhea) will also be captured in the AE eCRF. (revised per Amendment 01)

9.5.1.5.9 ELECTROCARDIOGRAMS

Twelve-lead ECGs will be obtained as designated in the Schedule of Procedures/Assessments ([Table 2](#)).

An ECG abnormality may meet the criteria of an AE as described in this protocol (see [Section 9.5.1.5.1](#)) and the CRF Completion Guidelines. In these instances, the AE corresponding to the ECG abnormality will be recorded on the Adverse Events CRF.

For ECG abnormalities meeting criteria of an SAE (see [Section 9.5.1.5.2](#)), the site must fax or email the SAE report including the ECG report to the sponsor using the SAE form (see [Section 9.5.4.1](#)).

9.5.1.5.10 OTHER SAFETY ASSESSMENTS

Leiter-3

The Leiter International Performance Scale–Third Edition (Leiter-3) is widely used non verbal measure of intelligence, memory, and attention in those between the ages of 3 and 75 years. The Attention/Memory Battery consists of 5 subtests: 2 measure nonverbal attention; 2 measure memory; and 1 measures cognitive interference (nonverbal Stroop test). These subtests are combined to produce a Memory and Processing Speed composite scores, normalized to a mean of 100 and standard deviation of 15. The Leiter-3 will be used to assess lorcaserin effects on cognition, specifically, attention and memory. In addition, signs and symptoms of cognition-related AEs, including impairments in attention, memory, and adverse effects on schoolwork will be captured in the eCRF. (revised per Amendment 01)

PHQ-9

The PHQ-9 is a multipurpose instrument for screening, diagnosing, monitoring and measuring the severity of depression:

- The PHQ-9 incorporates Diagnostic and Statistical Manual of Mental Disorders, 4th Edition (DSM-IV) depression diagnostic criteria with other leading major depressive symptoms into a brief self-report tool.
- The tool rates the frequency of the symptoms which factors into the scoring severity index.
- Question 9 on the PHQ-9 screens for the presence and duration of suicide ideation.
- A follow-up, non-scored question on the PHQ-9 assigns weight to the degree to which depressive problems have affected the patient's level of function.

C-SSRS

The C-SSRS collects information pertinent to suicidal ideation and actions. It consists of a Baseline version which will be administered at baseline and a Since Last Visit version which will be administered at the remaining visits. C-SSRS will be used to assess signal of depression and suicidal ideation or behavior. Qualified personnel must evaluate positive responses on the C-SSRS and take appropriate action as detailed in the training and certification process for administering the C-SSRS. It will be performed at Screening and at study visits as designated in the Schedule of Procedures/Assessments ([Table 2](#)). (revised per Amendment 01)

Hand X-Ray

A hand x-ray for evaluation of any potential negative effect on bone age will be performed on the same hand at each visit as designated in the Schedules/Assessments ([Table 2](#)). (revised per Amendment 01)

Tanner Staging

The pubic hair growth (both sexes), genital (males only) and breast (females only) development of subjects will be using Tanner Staging ([Marshall, 1970](#)). Subjects will be examined by the investigator as designated in the Schedules/Assessments ([Table 2](#)). (revised per Amendment 01)

Echocardiogram

Echocardiograms will be obtained on the Schedule of Procedures/Assessments ([Table 2](#)). Valvular regurgitation in echocardiogram will be rated absent, trace, mild, moderate, or severe for the aortic, mitral, and tricuspid valves; the rating will be absent or present for the pulmonic valve. The evaluations will be based on guidelines from the American Society of Echocardiography. Pulmonary artery pressure will be estimated from the TR regurgitant jet velocity.

9.5.1.6 Other Assessments**9.5.1.6.1 PREGNANCY TEST**

A urine pregnancy test in female subjects will be performed at designated time points as specified in the Schedule of Procedures/Assessments ([Table 2](#)).

9.5.2 Schedule of Procedures/Assessments**9.5.2.1 Schedule of Procedures/Assessments**

[Table 2](#) presents the Schedule of Procedures/Assessments for the study.

Table 2 Schedule of Procedures/Assessments in Study APD356-A001-403 (revised per Amendments 01 and 02)															
Phase:	Prerandomization^a	Randomization													
Period:	Screening	Treatment											Follow-Up		
Visit Number:	1	2 ^a	3	4	5	6	7	8	9	10	11 (EOT)	EOS	US ^b	ED	
Day:	-30 to -1	1													
Weeks^{c,d}:		0	1	5	8	12	20	28	36	44	52	56			
Procedure															
Informed Consent	X														
Demography	X														
Medical History	X														
Prior/concomitant medication assessments	X	X	X	X	X	X	X	X	X	X	X	X	X	X	
AE monitoring	X	X	X	X	X	X	X	X	X	X	X	X	X	X	
Inclusion/exclusion criteria	X	X													
Physical Examination ^e	X	X	X			X		X			X	X	X	X	
Vital signs	X	X	X	X	X	X	X	X	X	X	X	X	X	X	
Height	X	X	X	X	X	X	X	X	X	X	X	X	X	X	
Weight	X	X	X	X	X	X	X	X	X	X	X	X	X	X	
Waist circumference	X	X		X		X		X	X		X	X	X	X	
CDC growth chart	X	X		X		X		X	X		X	X	X	X	
Tanner Staging	X	X						X			X	X	X	X	
Routine clinical laboratory tests	X	X	X	X		X		X			X	X	X	X	
Urinalysis	X	X	X	X		X		X			X	X	X	X	
Urine drug and cotinine test	X														
Fasting plasma glucose, insulin, and HbA1c sampling	X	X				X		X			X			X	
T4 and TSH	X							X			X			X	
Testosterone, Estradiol	X							X			X				

Phase:	Prerandomization ^a	Randomization													
Period:	Screening	Treatment											Follow-Up		
Visit Number:	1	2 ^a	3	4	5	6	7	8	9	10	11 (EOT)	EOS	US ^b	ED	
Day:	-30 to -1	1													
Weeks ^{c,d} :		0	1	5	8	12	20	28	36	44	52	56			
Procedure															
Pregnancy test (urine)	X	X	X	X	X	X	X	X	X	X	X	X		X	
Fasting prolactin	X	X				X		X			X			X	
OC, PICP, and Hydroxy-proline		X						X			X			X	
Fasting lipid panel		X						X			X			X	
Urine NTX		X						X			X			X	
PK/PD blood sampling						X		X	X		X ^f		X ^g	X ^f	
AM serum cortisol		X									X			X	
ECG		X						X			X	X		X	
Echocardiograph	X ^h							X			X			X	
Randomization		X													
IxRS	X	X		X	X	X	X	X	X	X	X				
Study drug dispensing		X		X	X	X	X	X	X	X			X		
Collect study medication				X	X	X	X	X	X	X	X	X	X	X	
Drug accounting and compliance			X	X	X	X	X	X	X	X	X		X	X	
Hand x-ray for bone age		X				X		X			X			X	
C-SSRS	X		X	X	X	X	X	X	X	X	X	X	X	X	
Leiter-3		X		X				X			X	X		X	
PHQ-9		X	X	X	X	X	X	X	X	X	X	X	X	X	
Standardized age-appropriate lifestyle modification counseling ⁱ		X	X	X	X	X	X	X	X	X			X		

Table 2 Schedule of Procedures/Assessments in Study APD356-A001-403 (revised per Amendments 01 and 02)															
Phase:	Prerandomization^a	Randomization													
Period:	Screening	Treatment											Follow-Up		
Visit Number:	1	2 ^a	3	4	5	6	7	8	9	10	11 (EOT)	EOS	US ^b	ED	
Day:	-30 to -1	1													
Weeks^{c,d}:		0	1	5	8	12	20	28	36	44	52	56			
Procedure															

AE = adverse event, AM = morning; CDC = Centers for Disease Control and Prevention, C-SSRS = Columbia-Suicide Severity Rating Scale, ECG = electrocardiogram, ED = early discontinuation, EOS = End of Study, EOT = End of Treatment, HbA_{1c} = hemoglobin A1c, IxRS = interactive voice or web response system, NTX = N-telopeptide, OC = osteocalcin; PHQ-9 = The Patient Health Questionnaire, PICP = carboxyterminal propeptide of type I procollagen, PD = pharmacodynamic, PK = pharmacokinetics, SAE = serious adverse event; T4 = thyroxine, TSH = thyroid stimulating hormone, US = unscheduled.

- ^a: Baseline measurements will be collected on Day 1, before drug administration unless specified otherwise.
- ^b: Unscheduled visits may be conducted at any time that additional assessments are indicated in the clinical judgment of the investigator. Note that not all assessments listed under Unscheduled Visit need to be conducted – actual assessments needed will be determined by the investigator and will be based on the specific visit needs. At Unscheduled Visits, PK samples should only be collected if subject has experienced a serious adverse event (SAE) while on study drug and the sample can be drawn within 60 hours of the initiation of the SAE. (revised per Amendment 01)
- ^c: Window ±7 days for all visits. (revised per Amendment 01)
- ^d: On the day of the Week 12, 28, and 52 clinic visits, subjects will be instructed not to take their study drug at home before the visit, but to bring their study drug to the clinic visit and take their daily dose at the clinic. Two blood samples for determination of plasma concentrations of lorcaserin will be taken: 1 predose (within 30 minutes before dosing) and 1 within 1 to 3 hours after dosing. Dose times must be recorded for the last 2 dosing times before the day of clinic visit. Week 52 PK samples should only be collected if the sample can be drawn within 60 hours of the last dose of study drug. On the day of the Week 36 clinic visit, subjects will take the morning dose at home, and will be asked to visit the clinic within 4 to 6 hours of dosing that day, during which 1 blood sample for PK assessments will be collected. Dose times must be recorded for the last 2 dosing times prior to the clinic visit. (revised per Amendment 01)
- ^e: Includes a neuromuscular assessment and signs and symptoms of priapism (painful erection) and hyperprolactinemia (menstrual cycle abnormalities or galactorrhea) (revised per Amendment 01)
- ^f: PK samples should only be collected if the sample can be drawn within 60 hours of the last dose of study drug.
- ^g: PK samples should only be collected if subject has experienced an SAE while on study drug and the sample can be drawn within 60 hours of the initiation of the SAE.
- ^h: Echocardiographic assessments will be performed during screening period after subjects have met all other inclusion and exclusion criteria.
- ⁱ: Lifestyle modification counseling will also be performed at Weeks 3, 16, 24, 32, 40, and 48 in addition to counseling at the scheduled visits in [Appendix 2](#).

